#### Non-English Speaking Subjects or Subjects from a Foreign Culture

Describe how information about the study will be communicated to potential subjects appropriate for their culture, and if necessary, how new information about the research may be relayed to subjects during the study.

Include contact information for someone who can act as a cultural consultant for your study. The person should be familiar with the culture of the subject population and/or be able to verify that translated documents are the equivalent of the English version of documents submitted. The consultant should not have any direct involvement with the study. If you do not know someone who would be willing to act as your cultural consultant, the Office of Research Integrity will try to find someone to fill this role (this may delay the approval process for your protocol). Please include the name, address, telephone number, and email of the person who will act as the cultural consultant for your study. For more details, see ORI's help page on [Research Involving Non-English Speaking Subjects or Subjects from a Foreign Culture](#).

For recruitment of Non-English speaking subjects, the consent document needs to be in the subject's native language. Download the informed consent template available in the E-IRB "Informed Consent/Assent Process" section and use it as a guide for developing the consent document. (Note: Your translated consent document can be attached to your application in the "Informed Consent" section; **be sure to save your responses in this section first.**)

If research is to be conducted at an international location, identify local regulations, laws, or ethics review requirements for human subject protection. If the project has been or will be reviewed by a local Ethics Committee, attach a copy of the review to the UK IRB using the attachment button below. You may also consult the current edition of the [International Compilation of Human Research Standards](#)

Does your study involve **HIV/AIDS research and/or screening for other reportable diseases (e.g., Hepatitis C, etc...)?**

Yes  No

#### HIV/AIDS Research

If you have questions about what constitutes a reportable disease and/or condition in the state of Kentucky, see ORI's summary sheet: "Reporting Requirements for Diseases and Conditions in Kentucky" [[PDF](#)].

**HIV/AIDS Research:** There are additional IRB requirements for designing and implementing the research and for obtaining informed consent. Describe additional safeguards to minimize risk to subjects in the space provided below.

For additional information, visit the online [IRB Survival Handbook](#) to download a copy of the Medical IRB's requirements for Protection of Human Subjects in Research Involving HIV Testing, and visit the [Office for Human Research Protections web site](#) for statements on AIDS research, or contact the Office of Research Integrity at [contact].

#### PI-Sponsored FDA-Regulated Research

Is this an investigator-initiated study that:

[Back to Top](#)

- 1) involves testing a Nonsignificant Risk (NSR) Device, or
- 2) is being conducted under an investigator-held Investigational New Drug (IND) or Investigational Device Exemption (IDE)?

Yes  No

#### PI-Sponsored FDA-Regulated Research

If the answer above is yes, then the PI assumes the regulatory responsibilities of both the investigator and sponsor. The Office of Research Integrity provides a summary list of sponsor [IND regulatory requirements for drug trials](#), [IDE regulatory requirements for SR device trials](#), and [abbreviated regulatory requirements for NSR device trials](#). For detailed descriptions see [FDA Responsibilities for Device Study Sponsors](#) or [FDA Responsibilities for IND Drug Study Sponsor-Investigators](#).

- Describe your (the PI's) experience/knowledge/training (if any) in serving as a sponsor (e.g., previously held an IND/IDE); and
- Indicate if you have transferred any sponsor obligations to a commercial sponsor, contract research organization (CRO), contract monitor, or other entity (provide details or attach FDA 1571).

IRB policy requires mandatory training for all investigators who are also FDA-regulated sponsors (see [Sponsor-Investigator FAQs](#)). A sponsor-investigator must complete the applicable Office of Research Integrity web based training, (drug or device) before final IRB approval is granted.

Has the PI completed the mandatory PI-sponsor training prior to this submission?

Yes  No

If you (the PI) have completed equivalent sponsor-investigator training, you may submit documentation of the content for the IRB's consideration.

[Attachments](#)

**HIPAA**

Is HIPAA applicable?  Yes  No

(Visit ORI's [Health Insurance Portability and Accountability Act \(HIPAA\) web page](#) to determine if your research falls under the HIPAA Privacy Regulation.)

If yes, check below all that apply and attach the applicable document(s): 

- HIPAA De-identification Certification Form
- HIPAA Waiver of Authorization

**Attachments**

**STUDY DRUG INFORMATION****The term drug may include:**

- FDA approved drugs,
- unapproved use of approved drugs,
- investigational drugs or biologics,
- other compounds or products intended to affect structure or function of the body, and/or
- [complementary and alternative medicine products](#) such as dietary supplements, substances generally recognized as safe (GRAS) when used to diagnose, cure mitigate, treat or prevent disease, or clinical studies of [e-cigarettes](#) examining a potential therapeutic purpose.

**Does this protocol involve any use of a drug in a human other than the use of an approved drug in the course of medical practice?**

Yes  No

If yes, complete the questions below. Additional study drug guidance [\[HTML\]](#)

LIST EACH DRUG INVOLVED IN STUDY IN THE SPACE BELOW

Drug Name:

Scopolamine patch

Note: Inpatient studies are required by Hospital Policy to utilize the Investigational Drug Service (IDS). Use of IDS is highly recommended, but optional for outpatient studies. Outpatient studies not using IDS services are subject to periodic inspection by the IDS for compliance with drug accountability good clinical practices.

Indicate where study drug(s) will be housed and managed:

Investigational Drug Service (IDS) UK Hospital

Other Location:

Is the study being conducted under a valid Investigational New Drug (IND) application?

Yes  No

If Yes, list IND #(s) and complete the following:

IND Submitted/Held by:

Sponsor:

Held By:

Investigator:

Held By:

Other:

Held By:

Checkmark this if the study is being conducted under FDA's Expanded Access Program (e.g., Treatment IND).

- [FDA's Expanded Access Program Information \(e.g., treatment IND\)](#)
- Guidance and definitions: "Expanded Access SOP" [\[PDF\]](#)

**Please also complete and attach the Study Drug Form (required):**

[\[PDF\]](#)

## Attachments

Attach Type	File Name
StudyDrug	Study Drug Attachment INCREASE.pdf
StudyDrug	Transderm Scop Package Insert.pdf

## STUDY DEVICE INFORMATION

### A DEVICE may be a:

- component, part, accessory;
- assay, reagent;
- software or computer/phone application;
- other instrument if intended to affect the structure or function of the body, diagnose, cure, mitigate, treat or prevent disease; or
- a homemade device developed by an investigator or other non-commercial entity and not approved for marketing by FDA.

For additional information, helpful resources, and definitions, see ORI's [Use of Any Device Being Tested in Research web page](#).

### Does this protocol involve testing (collecting safety or efficacy data) of a medical device including an FDA approved device, unapproved use of an approved device, humanitarian use device, and/or an investigational device?

Yes  No

[Note: If a marketed device(s) is only being used to elicit or measure a physiologic response or clinical outcome, AND, NO data will be collected on or about the device itself, you may answer "no" above, save and exit this section, (Examples: a chemo drug study uses an MRI to measure tumor growth but does NOT assess how effective the MRI is at making the measurement; an exercise study uses a heart monitor to measure athletic performance but no safety or efficacy information will be collected about the device itself, nor will the data collected be used for comparative purposes against any other similar device).]

If you answered yes above, please complete the following questions.

#### LIST EACH DEVICE BEING TESTED IN STUDY IN THE SPACE BELOW

Device Name:

Is the study being conducted under a valid Investigational Device Exemption (IDE) or Humanitarian Device Exemption (HDE) application? See UK HUD SOP [\[PDF\]](#) for guidance.

Yes  No

If Yes, list IDE or HDE #(s) and complete the following:

IDE/HDE Submitted/Held by:

Sponsor:

Held By:

Investigator:

Held By:

Other:

Held By:

Check if this is a Treatment or Compassionate Use IDE under the Food and Drug Administration (FDA) Early Expanded Access program.

- [FDA's Early Expanded Access Program Information](#)
- Guidance and definitions: "Medical Device Clinical Investigations, Compassionate Use, and Treatment IDE SOP" [\[PDF\]](#)

Does the intended use of any device used in this study meet the regulatory [definition](#) of Significant Risk (SR) device?

Yes. Device(s) as used in this study presents a potential for serious risk to the health, safety, or welfare of a subject and (1) is intended as an implant; or (2) is used in supporting or sustaining human life; or (3) is of substantial importance in diagnosing, curing, mitigating or treating disease, or otherwise prevents impairment of human health; or (4) otherwise presents a potential

for serious risk to the health, safety, or welfare of a subject.

No. All devices, as used in this study do not present a potential for serious risk to the health, safety, or welfare of subjects/participants.

Please also complete and attach the Study Device Form (required):

[\[PDF\]](#)

Attachments

**RESEARCH SITES**

In order for this section to be considered complete, you must click "SAVE" after ensuring all responses are accurate.

A) Check all the applicable sites listed below at which the research will be conducted. If none apply, you do not need to check any boxes.

UK Sites

- UK Classroom(s)/Lab(s)
- UK Clinics in Lexington
- UK Clinics outside of Lexington
- UK Healthcare Good Samaritan Hospital
- UK Hospital

Schools/Education Institutions

- Fayette Co. School Systems \*
- Other State/Regional School Systems
- Institutions of Higher Education (other than UK)

**\*Fayette Co. School systems, as well as other non-UK sites, have additional requirements that must be addressed. See ORI's [Off-site Research Instructions web page](#) for details.**

Other Medical Facilities

- Bluegrass Regional Mental Health Retardation Board
- Cardinal Hill Hospital
- Eastern State Hospital
- Norton Healthcare
- Nursing Homes
- Shriner's Children's Hospital
- Veterans Affairs Medical Center
- Other Hospitals and Med. Centers

- Correctional Facilities
- Home Health Agencies
- International Sites

List all other non-UK owned/operated locations where the research will be conducted:\*

\*A letter of support and local context is required from non-UK sites. Click [HERE](#) for more information.

Attachments

B) Is this a multi-site study for which you are the lead investigator or UK is the lead site?  Yes  No

If **YES**, you must describe the plan for the management of reporting unanticipated problems, noncompliance, and submission of protocol modifications and interim results from the non-UK sites in the E-IRB "Research Description" section under *Resources*.

If the non-UK sites or non-UK personnel are *engaged* in the research, there are additional federal and university requirements which need to be completed for their participation, such as the establishment of a cooperative IRB review agreement with the non-UK site. Questions about the participation of non-UK sites/personnel should be discussed with the ORI staff at [contact].

## RESEARCH ATTRIBUTES

Indicate the items below that apply to your research. Depending on the items applicable to your research, you may be required to complete additional forms or meet additional requirements. Contact the ORI [contact]) if you have questions about additional requirements.

Not applicable

### Check All That Apply

- Academic Degree/Required Research
- Aging Research
- Alcohol Abuse Research
- Cancer Research
- Certificate of Confidentiality
- CCTS-Center for Clinical & Translational Science
- Clinical Research
- Clinical Trial
- Clinical Trial Multicenter(excluding NIH Cooperative Groups)
- Clinical Trial NIH cooperative groups (i.e., SWOG, RTOG)
- Clinical Trial Placebo Controlled Trial
- Clinical Trial UK Only
- Collection of Biological Specimens
- Collection of Biological Specimens for Banking
- Community-Based Participatory Research
- Data & Safety Monitoring Board
- Data & Safety Monitoring Plan
- Deception
- Drug/Substance Abuse Research
- Educational/Student Records (e.g., GPA, test scores)
- Emergency Use (Single Patient)
- Genetic Research
- Gene Transfer
- GWAS (Genome-Wide Association Study) or NIH-funded study generating large scale genomic data
- International Research
- Internet Research
- Planned Emergency Research Involving Waiver of Informed Consent
- Pluripotent Stem Cell Research
- Recombinant DNA
- Survey Research
- Transplants
- Use of radioactive material, ionizing radiation, or x-rays [Radiation Safety Committee review required]
- Vaccine Trials

Click applicable listing(s) for additional requirements and/or information:

- [Cancer Research \(MCC PRMC\)](#)
- [Certificate of Confidentiality](#)
- [CCTS \(Center for Clinical and Translational Science\)](#)
- [Clinical Research](#)
- [Clinical Trial](#)

Determine if research meets [NIH definition of clinical trial](#);

\*Reminder: Ensure compliance with [clinicaltrials.gov](#) registration requirements for applicable clinical trials and [Good Clinical Practice \(GCP\) training](#) requirements.

- [Collection of Biological Specimens for Banking](#)
- [Collection of Biological Specimens](#)
- [Community-Based Participatory Research](#)
- [Data & Safety Monitoring Board](#)
- [Data & Safety Monitoring Plan](#)
- [Deception\\*](#)

\*For deception research, also go to the Informed Consent section, checkmark and complete "Request for Waiver of Informed Consent Process"

- [Emergency Use \(Single Patient\) \[attach Emergency Use Checklist\]](#)
- [Genetic Research](#)
- [Gene Transfer](#)
- [HIV/AIDS Research](#)
- [Screening for Reportable Diseases \[E2.0000\]](#)
- [International Research](#)
- [Planned Emergency Research Involving Waiver of Informed Consent\\*](#)

\*For Planned Emergency Research Involving Waiver of Informed Consent, also go to the Informed Consent section, checkmark and complete "Request for Waiver of Informed Consent Process"

- [Use of radioactive material, ionizing radiation or x-rays for research](#)

## FUNDING/SUPPORT

If the research is being submitted to, supported by, or conducted in cooperation with an external or internal agency or funding program, indicate below all the categories that apply. [i](#)

Not applicable

### Check All That Apply

- Grant application pending
- (HHS) Dept. of Health & Human Services
- (NIH) National Institutes of Health
- (CDC) Centers for Disease Control & Prevention
- (HRSA) Health Resources and Services Administration
- (SAMHSA) Substance Abuse and Mental Health Services Administration
- (DoJ) Department of Justice or Bureau of Prisons
- (DoE) Department of Energy
- (EPA) Environmental Protection Agency
- Federal Agencies Other Than Those Listed Here
- Industry (Other than Pharmaceutical Companies)
- Internal Grant Program w/ proposal
- Internal Grant Program w/o proposal
- National Science Foundation
- Other Institutions of Higher Education
- Pharmaceutical Company
- Private Foundation/Association
- U.S. Department of Education
- State

Other:

Specify the funding source and/or cooperating organization(s) (e.g., National Cancer Institute, Ford Foundation, Eli Lilly & Company, South Western Oncology Group, Bureau of Prisons, etc.):

Click applicable listing(s) for additional requirements and/or information:

- [\(HHS\) Dept. of Health & Human Services](#)
- [\(NIH\) National Institutes of Health](#)
- [\(CDC\) Centers for Disease Control & Prevention](#)
- [\(HRSA\) Health Resources & Services Administration](#)
- [\(SAMHSA\) Substance Abuse & Mental Health Services Administration](#)
- Industry (Other than Pharmaceutical Companies) [[IRB Fee Info](#)]
- [National Science Foundation](#)
- [\(DoEd\) U.S. Department of Education](#)
- [\(DoJ\) Department of Justice or Bureau of Prisons](#)
- [\(DoE\) Department of Energy](#)
- [\(EPA\) Environmental Protection Agency](#)

### Add Related Grants

If applicable, please search for and select the OSPA Account number or Electronic Internal Approval Form (eIAF) # (notif #) associated with this IRB application:

The research involves use of Department of Defense (DoD) funding, military personnel, DoD facilities, or other DoD resources. (See DoD SOP [\[PDF\]](#) for details).

Yes  No

Using the "attachments" button (below), attach applicable materials addressing the specific processes described in the DoD SOP.

Additional Certification: (If your project is federally funded, your funding agency may request an Assurance/ Certification/Declaration of Exemption form.) Check the following if needed:

Protection of Human Subjects Assurance/Certification/Declaration of Exemption (Formerly Optional Form – 310)

## OTHER REVIEW COMMITTEES

If you check any of the below committees, additional materials may be required with your application submission.

Does your research fall under the purview of any of the other review committees listed below? *[If yes, check all that apply and attach applicable materials using the attachment button at the bottom of your screen.]*

Yes  No

### Additional Information

- Institutional Biosafety Committee
- Radiation Safety Committee
- Radioactive Drug Research Committee
- Markey Cancer Center (MCC) Protocol Review and Monitoring Committee (PRMC)
- Graduate Medical Education Committee (GME)
- Office of Medical Education (OME)

- Institutional Biosafety Committee (IBC)--Attach [required IBC materials](#)
- Radiation Safety Committee (RSC)-- For applicability, see [instructions](#) and/or upload form [\[WORD\]](#) [\[RTF\]](#)
- Radioactive Drug Research Committee (RDRC)--[information](#)
- Markey Cancer Center (MCC) Protocol Review and Monitoring Committee (PRMC)\*\*--Attach MCC PRMC materials, if any, per [instructions](#)
- See requirement of [Office of Medical Education \(OME\)](#)
- See requirement of [Graduate Medical Education Committee \(GME\)](#)

**\*\* If you are proposing a study involving cancer research, be sure to have "Cancer Research" marked in the E-IRB "Research Attributes" section.** If your study involves cancer research, ORI will provide a copy of your research protocol to the Markey Cancer Center (MCC) Protocol Review and Monitoring Committee (PRMC). The [MCC PRMC](#) is responsible for determining whether the study meets the National Cancer Institute (NCI) definition of a clinical trial and for issuing documentation to you (the investigator) which confirms either that PRMC approval has been obtained or that PRC review is not required. Your IRB application will be processed and reviewed independently from the PRMC review.

**ADDITIONAL INFORMATION/MATERIALS**

Do you want specific information inserted into your approval letter?  Yes  No

Approval Letter Details (e.g., serial #):

Submission Description: If you wish to have specific details included in your approval letter (e.g., serial #, internal tracking identifier, etc...), provide that information here as you wish it to be seen on the approval letter. These details will be automatically merged into a field at the top of the approval letter when it is generated. If these details need to be changed as a result of revisions or modifications to the application, you are responsible for updating the content of the field below accordingly.

Protocol/Product Attachments - For each item checked, please attach the corresponding material.

- Detailed protocol
- Dept. of Health & Human Services (DHHS) approved protocol (such as NIH sponsored Cooperative Group Clinical Trial)
- Drug Documentation (e.g., Investigator Brochure; approved labeling; publication; FDA correspondence, etc.)
- Device Documentation (e.g., Manufacturer information; patient information packet; approved labeling; FDA correspondence, etc.)
- Other Documents

**Protocol/Product Attachments**

NOTE: Instructions for Dept. of Health & Human Services (DHHS)-approved protocol [[HTML](#)]

**If you have password protected documents, that feature should be disabled prior to uploading to ensure access for IRB review.**

Additional Materials:

If you have other materials you would like to include in your application for the IRB's consideration, please attach using the Attachments button below.

[To view what materials are currently attached to your application, go to "Application Links" in the menu bar on the left and click "All Attachments".]

**Attachments**

Attach Type	File Name
AdditionInfoConsiderations	CR 16-0375-F2L SN017.pdf
AdditionInfoConsiderations	INCREASE Form T.PDF

**SUBMISSION INFORMATION**

Each Section/Subsection in the menu on the left must have a checkmark beside it indicating the Section/Subsection has been completed; otherwise your submission for IRB review and approval will not be able to be sent to the Office of Research Integrity/IRB.

If your materials require review at a convened IRB meeting which you will be asked to attend, it will be scheduled on the next available agenda and a message will be forthcoming to notify you of the date.

Your protocol has been submitted.

**The PI must login to submit this protocol.**

	Document Type	File Loaded	Document Description	File Size	Modified By	Mod Date
⚡	ApprovalLetter	ApprovalLetter.pdf		0.059	pkma223	3/6/2018 3:56:01 PM
⚡	Stamped Consent Form	INCREASE Form C V5.pdf		0.222	pkma223	3/6/2018 3:56:01 PM
⚡	AdditionInfoConsiderations	INCREASE Form T.PDF	Form T	0.224	pkma223	1/31/2018 3:56:02 PM
⚡	AdditionInfoConsiderations	CR 16-0375-F2L SN017.pdf	Continuation Review 2018	2.245	bfbe223	1/11/2018 10:18:21 AM
⚡	DataCollection	11 - EOS Questionnaire.docx		0.015	bfbe223	1/9/2018 5:17:46 PM
⚡	DataCollection	17 - Baseline Questionnaire.docx		0.018	bfbe223	1/9/2018 5:17:32 PM
⚡	DataCollection	16 - SF-36.pdf	SF-36	0.064	bfbe223	1/9/2018 5:16:55 PM
⚡	DataCollection	Lifestyles Survey_Follow-Up.docx	EOS Lifestyles Survey	0.091	bfbe223	1/9/2018 5:16:24 PM
⚡	DataCollection	Lifestyles Survey_V6.0_Initial Packet.docx	Initial Lifestyles Survey	0.062	bfbe223	1/9/2018 5:15:59 PM
⚡	DataCollection	INCREASE Study Procedures.pdf		0.261	bfbe223	1/9/2018 5:15:10 PM
⚡	Advertising	INCREASE Recruitment Letter Version 5 CLEAN.pdf		0.045	bfbe223	12/19/2017 12:45:36 PM
⚡	Advertising	INCREASE_flyer_Version_3.pdf		1.191	bfbe223	12/19/2017 12:45:22 PM
⚡	StudyDrug	Transderm Scop Package Insert.pdf		0.543	bfbe223	12/19/2017 9:34:20 AM
⚡	StudyDrug	Study Drug Attachment INCREASE.pdf		0.304	bfbe223	12/19/2017 9:32:16 AM
⚡	Informed ConsentHIPAA Combined Form	INCREASE Form C V5.pdf		0.100	bfbe223	12/18/2017 4:04:52 PM

## Protocol Changes

Protocol Number: 43239

No Changes

There are no recorded changes tracked for this protocol.

## Study Personnel Changes:

No Changes

There are no recorded changes to study personnel.

Study Title: Intervention for Cognitive Reserve Enhancement in delaying the onset of Alzheimer's Symptomatic Expression (INCREASE) Study

ClinicalTrials.gov NCT02849639

Developed: December 14, 2015

Statistical analyses

We will use Student's t-tests (or Wilcoxon rank sum tests for non-normally distributed variables) and chi-square or Fisher's exact tests to assess the comparability of randomized study groups. To examine the effect of the intervention on prescribing appropriateness we will perform analysis of covariance (ANCOVA), with the dependent variables being the difference between MAI scores at baseline and the follow-up measure. We will control for any variables that might be significantly different between groups at baseline that have not already been included in the study protocol in regards to stratification of subjects.

Data evaluating cognitive reserve will be analyzed by intervention groups. For Aim 2, the impact on cognitive reserve will be assessed across the full range of SUVR (i.e., SUVR will be included in the analysis as continuous variable). If imbalance exists between groups after randomization, covariates for analysis will include age, gender, education, NART scores, and the number of targeted inappropriate medications using 2015 Beers Criteria. We will investigate change from baseline in CRCS by group using ANCOVA.

For the perceived health status measure, because the SF-36 does not produce a single overall measure and because of our concern regarding multiple comparisons, multivariate analysis of covariance (MANCOVA) will be used to simultaneously estimate the effect of the intervention on the eight SF-36 health concepts. Similarly, we will also control for any variables that might be significantly different between groups at baseline.

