**Objectives:** List your research objectives. You may reference grant application/sponsor's relevant protocol pages and attach as an appendix in the E-IRB "Additional Information" section.

Specific Aim 1: Conduct a 12-month, randomized, placebo-controlled trial to evaluate the impact of our patient-centered, pharmacist-physician team MTM intervention in reducing unnecessary and inappropriate medication use in community-dwelling, elderly, non-demented subjects. Our team will specifically target the Beers 2015 list of inappropriate medications for those 65 years and older, and implement individualized, patient-centered alternative management strategies. Primary outcome measures will include pre- to post- intervention measures of: (1) use of inappropriate medications as measured by the Medication Appropriateness Index (MAI); 2) Cognitive Reserve Change Score (CRCS), defined as the difference in the scopolamine- challenged vs unchallenged measures on the neurocognitive score (defined below). Specific Aim 2: Evaluate the impact of preclinical amyloid burden on cognitive reserve deficits and decline (measured as CRCS) to evaluate efficacy of delaying symptomatic disease progression in pAD. Baseline determination of total brain relative standardized uptake values for amyloid  $\beta$ - positron emission tomography will be used to examine the relative impact of preclinical AD pathology on CRCS at baseline and over time in the placebo group, as well as the interplay of pAD pathology with inappropriate medication use at baseline and optimization of medication use after one year of MTM intervention. Objectives: 1) Examine the effectiveness of the MTM intervention in reducing inappropriate medication use over the study period as assessed by the MAI (Aim 1). 2) Investigate the effects of baseline A $\beta$ -PET and medication appropriateness index (MAI) 35 on cognitive reserve, operationalized as the CRCS = scopolamine challenged test performance z score - unchallenged cognitive test performance z score (Aim 1 and 2). 3) Investigate the effects of MTM and changes in MAI on CRCS in subjects that are A $\beta$ -PET positive or negative over the one-year study period (Aim 1 and 2).

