**Study Design:** Describe the study design (e.g., single/double blind, parallel, crossover, etc.). Indicate whether or not the subjects will receive placebo medication at some point in the research procedures. Also, indicate whether or not the subjects will be randomized in this study. You may reference sponsor's protocol pages and attach as an appendix in the E-IRB "Additional Information" section. (Including the study design table from a sponsor's protocol is helpful to IRB members.)

**Community-Based Participatory Research:** If you are conducting [community-based participatory research \(CBPR\)](#), describe strategies for involvement of community members in the design and implementation of the study, and dissemination of results from the

study.

**Research Repositories:** If the purpose of this submission is to establish a research repository describe the repository design and operating procedures. For relevant information to include, see question 22 of the UK IRB “Frequently Asked Questions (FAQs) on the Return of Research Results or Incidental Research Findings” [\[PDF\]](#).

This is a 12-month, parallel arm, placebo-controlled study to be conducted at the University of Kentucky. 90 non-demented subjects with varying levels of A $\beta$ -PET positivity (estimated that 30 will meet threshold criteria for pAD) will be randomly assigned to treatment with the MTM intervention or placebo. Those assigned in the intervention arm might have medication changes recommended by the research team. A letter describing all the proposed changes will be sent to the participant’s primary care physician (PCP). These changes will be recommended, but not forced on the participant and their PCP. The participant and their PCP will have final decision on accepting or rejecting the proposed changes in the medication plan. All subjects will undergo cognitive testing under both scopolamine challenged and unchallenged conditions within 4 weeks, as well as physical and neurologic exam, and A $\beta$ -PET scan at baseline. Cognitive testing under both scopolamine challenged and unchallenged conditions within 4 weeks, as well as physical and neurologic exam will be performed at study completion. Randomization will be stratified by A $\beta$  positivity on PET scans. If unbalanced between groups after randomization, age, gender, education, NART, and number of targeted inappropriate medications using Beers 2015 Criteria will be included in the analyses.

Attachments

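### The SAP does not make baseline MAI and baseline CRCS standing covariates in the two primary change analyses, so precision can be lost

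*SAP*

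**What the plan says.** The protocol (Research Description, Objectives) introduces MAI and CRCS with "Primary outcome measures will include pre- to post- intervention measures of", so both are primary and both are measured as change.

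The SAP (Statistical analyses) treats them as follows.

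- **MAI, model:** "we will perform analysis of covariance (ANCOVA), with the dependent variables being the difference between MAI scores at baseline and the follow-up measure".
- **MAI, covariates:** "We will control for any variables that might be significantly different between groups at baseline", limited to those "that have not already been included in the study protocol in regards to stratification of subjects".
- **CRCS, model:** "We will investigate change from baseline in CRCS by group using ANCOVA".
- **CRCS, covariates:** "If imbalance exists between groups after randomization, covariates for analysis will include age, gender, education, NART scores, and the number of targeted inappropriate medications" by the 2015 Beers Criteria.

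The protocol gives the same conditional list under Study Design ("If unbalanced between groups after randomization, age, gender, education, NART, and number of targeted inappropriate medications using Beers 2015 Criteria will be included") and again in the randomisation text under Research Procedures. Neither place adds baseline MAI or baseline CRCS. Objective 2 uses baseline MAI as an explanatory variable for cognitive reserve, but that does not make it a covariate in the MAI-change model.

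**The concern.** When a change score is compared between randomised arms, the participant's own baseline is usually the most useful covariate, because change is correlated with the starting value. Here no sentence puts it in the model. For MAI it is assured entry only after a significant baseline test. For CRCS it is not on the list at all. If no imbalance is found, the written rules can leave a two-sample comparison of change under the name ANCOVA.

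The validity of the test is not in question: that comparison is unbiased on average under randomisation and its type I error stays near 5%. What is at stake is a wider confidence interval and lower power on both primary outcomes in a trial of 90 people. There is also some ambiguity about which model is primary, since two analysts could fit different models and both claim to have followed the SAP.

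**Working it through.** **The plan's own figure.** The only design figure is 90 participants (protocol, Study Population). No alpha, power, effect size, SD, dropout or correlation comes with it, so it cannot be reproduced.

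**Inputs.** From the documents: 90 participants and two randomised arms. Assumed: 45 per arm, no dropout, two-sided 0.05, and the same SDs and slope in both arms. The baseline to follow-up correlation ρ and the SD ratio k (follow-up SD over baseline SD) are not given, so ranges are used. The effect is set to give 80% power with baseline adjustment, as a reference point only.

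**Variance.** Take the baseline SD as 1.

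- Unadjusted change: variance 1 + k² − 2ρk.
- Adjusted for baseline: residual variance k²(1 − ρ²).
- Ratio unadjusted/adjusted: (1 + k² − 2ρk) / (k²(1 − ρ²)), which is 2/(1 + ρ) at k = 1.

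**Power.** With adjustment there are 87 df, and 80% power needs a noncentrality of 2.833. Without adjustment there are 88 df, and the noncentrality is 2.833 divided by the square root of the variance ratio. Example at ρ = 0.5, k = 1: ratio 2/1.5 = 1.333, square root 1.155, noncentrality 2.833/1.155 = 2.453, power 68.0%.

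| k | | ρ = 0.3 | ρ = 0.5 | ρ = 0.7 | ρ = 0.9 |
|---|---|---|---|---|---|
| 1.0 | variance ratio | 1.54 | 1.33 | 1.18 | 1.05 |
| | unadjusted power, % | 61.8 | 68.0 | 73.3 | 78.0 |
| 0.8 | variance ratio | 1.99 | 1.75 | 1.59 | 1.64 |
| | unadjusted power, % | 51.0 | 56.3 | 60.3 | 58.9 |
| 1.2 | variance ratio | 1.31 | 1.15 | 1.03 | 1.02 |
| | unadjusted power, % | 68.6 | 74.4 | 78.7 | 79.1 |

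The loss runs from 80 − 79.1 = 0.9 points to 80 − 51.0 = 29.0 points. At k = 1, the unadjusted analysis would need 90 × ratio = about 138, 120, 106 and 95 people to match 90 with adjustment. With 38 completers per arm the powers are the same to the nearest percent.

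**Does the MAI rule recover the loss?** It was simulated with 200,000 trials per cell, baseline entering only if its between-arm p is below 0.05. The SAP does not state the threshold, so 0.05 is an assumption. Baseline entered in 5.0 to 5.1% of trials. Power at k = 1 was 63.0, 68.9, 73.9 and 78.1%, against 79.3 to 79.6% when baseline always entered. Almost nothing is recovered. Type I error was 3.6 to 4.9% under the triggered rule and about 5.0% for the other two analyses.

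**Do other covariates stand in for baseline?**

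- Amyloid stratum in both models, unrelated to outcome: the k = 1 powers do not change.
- Beers-drug count always in the MAI model, with assumed correlation q to baseline MAI and linked to follow-up only through it: the ratio at k = 1 is (2(1 − ρ) − q²(1 − ρ)²)/(1 − ρ²). At q = 0.5 this is 1.40, 1.25, 1.13 and 1.04, with power 65.7, 70.7, 74.9 and 78.5%. The recovery is partial, and the documents make entry of the count conditional.

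**In a single realised trial.** A chance baseline gap moves the unadjusted estimate by (1 − ρk) × gap, against the direction of the gap when ρk < 1. A gap of 0.3 SD has p = 0.16, so the significance rule would not react to it. At k = 1 it shifts the estimate by 0.21, 0.15, 0.09 and 0.03 baseline SDs at the four values of ρ. This is how the extra variance arises and is not a second cost.

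**The case against.** The best reply is that ANCOVA already implies baseline adjustment. The SAP specifies it unconditionally for both outcomes while the other covariates it names for them are conditional. If baseline is not the standing covariate, the MAI model may contain none. Adjusting for baseline is also the ordinary reason to choose ANCOVA for pre/post data. That may well be what was meant, and the gap is then one of wording.

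The word does not settle it, for three reasons. The dependent variable is already a difference from baseline, so an analyst may think baseline has been dealt with. The covariate rule that follows the MAI model is conditional, and its stratification clause leaves room for amyloid status to be the covariate in mind, though it does not say so. The SF-36 paragraph pairs MANCOVA with the same conditional rule ("Similarly, we will also control for any variables that might be significantly different between groups at baseline"), so the label does not reliably signal own-baseline adjustment in this SAP.

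Two further points stand. No loss is established for this trial: ρ, k and the 80% reference are not in the documents, and the 29-point figure needs both ρ = 0.3 and k = 0.8. And both analyses are legitimate randomised comparisons. These points limit the severity but do not remove the gap.

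The SAP also enters SUVR as a continuous variable for Aim 2. That does not replace baseline CRCS: with SUVR in both models the same variance formula applies, with ρ and k taken after adjustment for SUVR.

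**Conclusion.** The concern holds. As written, the SAP does not secure baseline MAI or baseline CRCS in its own primary model, and following the stated rules can give a less precise analysis of both outcomes. The consequence is lost precision only, with no bias on average and no inflation of type I error. Under the stated assumptions, power falls from 80% to between 51 and 79% across ρ from 0.3 to 0.9 and k from 0.8 to 1.2. With equal SDs it falls to 62, 68, 73 or 78%. If the correlation is high and the SDs do not shrink, the loss is negligible; if the correlation is low to moderate, it is substantial for 90 people. CRCS is a difference of two z scores from separate visits, so a low correlation is plausible, but no value is given. The SAP should be changed; confidence is medium because the authors may have intended the adjustment.

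**What to change.** State in the SAP that the MAI-change model always includes baseline MAI and the CRCS-change model always includes baseline CRCS, whatever any baseline comparison shows. The outcome can stay as change: once baseline is in the model, the arm effect is identical to that for the follow-up score. The handling of the other listed covariates is a separate matter and need not change for this point.

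The cost is SAP wording and one degree of freedom per model. No new data are needed, because both baseline values are already required to form the change scores; baseline CRCS comes from the week −4 and week 0 visits. If adjustment was always intended, the sentence simply records it.
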